# 10.2.5 Deaths, Serious Adverse Events, and Adverse Events Leading to Study Treatment Discontinuation

SAEs (including deaths) and AEs leading to study drug discontinuation will be presented in listing format. SAEs and AEs leading to study drug discontinuation will be summarized by SOC and PT.

[figure not shown]
In addition, for each treatment group, the event rate leading to per 100 patient-years of exposure will be calculated for each SOC and each PT for each treatment emergent SAE and TEAEs leading to discontinuation of study drug.

#### 10.2.6 Adverse Events of Special Interest

Adverse events of special interest will be summarized by SOC and PT and listing format and will be based on standard or company MedDRA queries (SMQs or CMQs).

Adverse events of special interest are categorized as follows:

- Serious infections
- Opportunistic infection excluding tuberculosis and herpes zoster
- Herpes Zoster
- Active Tuberculosis
- Anemia
- Neutropenia
- Lymphopenia
- Renal Dysfunction
- Hepatic disorders (including DILI)
- Malignancy
- Non-melanoma skin cancer (NMSC)
- Malignancy excluding NMSC
- Lymphoma
- Adjudicated MACE
- Adjudicated VTE
- Adjudicated gastrointestinal perforations
- Bone fractures
- Retinal detachment
- Serious hypersensitivity reactions

Detailed information about the search criteria is provided in Appendix B.

Tabular listings of selected adverse events of special interest will be provided. Possible malignancy will only be listed.

Information on the extent of herpes zoster infection involvement will be summarized as collected in the respective AE form.

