5.5 Withdrawal of Subjects and Discontinuation of Study

AbbVie may terminate this study prematurely, either in its entirety or at any site. The study may be discontinued or terminated in case of an unacceptable risk, any relevant toxicity, or a negative change in the risk/benefit assessment. This might include the occurrence of AEs with a character, severity or frequency that is new in comparison to the existing risk profile. In addition, data deriving from other clinical trials or toxicological studies which negatively influence the risk/benefit assessment might cause discontinuation or termination of the study. The investigator may also stop the study at their site if they have safety concerns. If AbbVie terminates the study for safety reasons, AbbVie will promptly notify the investigator. Advance notice is not required by either party if the study is stopped due to safety concerns.

Subjects can request to be discontinued from participating in the study at any time for any reason. The investigator may discontinue any subject's participation at any time for any reason.

Subjects must have study drug discontinued immediately if any of the following occur:

- The subject requests withdrawal from study drug or the study.
- The investigator believes it is in the best interest of the subject.
- Abnormal laboratory results or AEs that either meet the criteria for discontinuation of study drug as stated in Section 6.2, or rule out safe continuation of the study drug.
- Serious infections (e.g., sepsis) which cannot be adequately controlled by anti-infective treatment or would put the subject at risk with continuation of the study drug.
- Confirmed diagnosis of deep vein thrombosis (DVT), pulmonary embolus (PE) or non-cardiac, non-neurologic arterial thrombosis.

- Subject is non-compliant with TB prophylaxis (if applicable) or develops active TB at any time during the study.
- Malignancy, except for localized NMSC or carcinoma in-situ of the cervix if this can be successfully treated at its localization
- Subject develops a gastrointestinal perforation (other than due to appendicitis or mechanical injury).
- The subject experiences a serious hypersensitivity reaction without an alternative etiology.
- The subject becomes pregnant while on study drug.
- Eligibility criteria violation was noted after the subject started study drug, when continuation of the study drug would place the subject at risk.

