AbbVie will be responsible for SUSAR reporting for the IMP in accordance with global and local requirements, including reporting to Eudravigilance database in accordance with EU Clinical Trial Regulation 536/2014.

Adverse events will be monitored throughout the study to identify any of special interest that may indicate a trend or risk to subjects.

Adverse Events of Special Interest

The following adverse events of special interest (AESIs) will be monitored during the study:

- Serious infections;
- Opportunistic infections;
- Herpes zoster;
- Active tuberculosis;
- Malignancy (all types);
- Anemia;
- Neutropenia;
- Lymphopenia;
- Renal dysfunction;
- Hepatic disorder;
- Adjudicated GI perforations;
- Adjudicated cardiovascular events (e.g., major adverse cardiovascular event [MACE]); and
- Adjudicated embolic and thrombotic events (non-cardiac, non-CNS).
- Fractures
- Retinal detachment

Cardiovascular Adjudication Committee

An independent external committee of physician experts in cardiovascular adjudication will be utilized to assess potential cardiovascular and thromboembolic AEs in a blinded manner as defined by the Cardiovascular Adjudication Committee charter.

Gastrointestinal Perforation Adjudication Committee

An internal GI perforation committee will identify and adjudicate AEs of spontaneous GI perforation. The internal committee will be comprised of at least 2 gastroenterologists or physicians with appropriate expertise who are independent of the clinical study team and blinded to subject treatment assignments. The committee's primary responsibility is to review potential events of GI perforation and adjudicate against a pre-specified case definition. A separate GI perforation charter will be prepared outside of the protocol and will describe the case definition, procedures, roles, and responsibilities.

Adverse Event Severity and Relationship to Study Drug

Investigators will rate the severity of each AE according to the National Cancer Institute Common Terminology Criteria for Adverse Events (NCI CTCAE Version 5.0), which can be accessed at: https://ctep.cancer.gov/protocolDevelopment/electronic applications/ctc.htm.

If no specific grading criteria are provided for the reported event, then the event should be as follows:

- Mild (Grade 1): asymptomatic or mild symptoms; clinical or diagnostic observations only; intervention not indicated;
- Moderate (Grade 2): minimal, local or noninvasive intervention indicated; limiting age

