6.2 Toxicity Management

The toxicity management of the AEs including AESIs consists of safety monitoring (review of AEs on an ongoing basis) and, if applicable, interruption of study drug dosing with appropriate clinical management and/or discontinuation of the subjects from study drug. The management of specific AEs and laboratory parameters is described below.

Serious Infections: Study drug should be interrupted if a subject develops a serious infection. A subject who develops a new infection during treatment with study drug should undergo prompt diagnostic testing appropriate for an immunocompromised subject. Study drug may be restarted once the infection has been successfully treated. Subjects who develop active TB must be permanently discontinued from study drug.

Herpes zoster: If a subject develops herpes zoster, consider temporarily interrupting study drug until the episode resolves.

Gastrointestinal Perforation: If a diagnosis of gastrointestinal perforation is confirmed (other than due to appendicitis or mechanical injury), the subject must be permanently discontinued from study drug.

Major cardiovascular event: For subjects who develop a major cardiovascular event (MACE: acute myocardial infarction, stroke) while on study drug, the investigator should evaluate the benefit/risk of, and discuss with the TA MD, whether it is appropriate to continue study drug.

Malignancy: Subjects who develop malignancy other than localized NMSC or carcinoma in situ of the cervix must be permanently discontinued from study drug. Information including histopathological results should be queried for confirmation of the diagnosis. Periodic skin examination is recommended for subjects who are at increased risk for skin cancer. Subjects who develop malignancies should be referred to appropriate specialists and managed as per standard of care.

Muscle-related symptoms: If a subject experiences symptoms suggestive of myositis or rhabdomyolysis, consider checking CPK and aldolase with clinical management and/or study drug interruption as deemed appropriate by the investigator.

Thrombosis Events: Subjects who develop symptoms of thrombosis should be promptly evaluated and treated appropriately. If the diagnosis of deep vein thrombosis (DVT), pulmonary embolus or non-cardiac, non-neurologic arterial thrombosis is confirmed, the subject must be discontinued from study drug.

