7.5 Statistical Analyses for Safety

The safety analyses will be summarized in the double-blind period, single-blind period, and across study periods by the upadacitinib doses, based on the Safety_1_SS1 and Safety_1_SS2 Populations, Safety_2_SS1 and Safety_2_SS2 Populations, and ALL_UPA Population, respectively.

Safety will be assessed by AEs, physical examination, laboratory assessments, and vital signs. Note that missing safety data will not be imputed. Analysis details will be specified in the SAP. Adverse events will be coded using the Medical Dictionary for Regulatory Activities (MedDRA). Treatment-emergent AEs in each period are defined as those that began or worsened in severity after the first dose of study drug in each period and up to the minimum of the end date of each period and 30 days after the last dose of the study drug in each period. The number and percentage of subjects experiencing TEAEs in each period

and across study periods by the upadacitinib doses will be tabulated using the MedDRA SOC and PT, by severity, and by relationship to the study drug as assessed by the investigator. Summaries (including number of subjects, percentages and events per 100 patient-years) of SAEs, deaths, AEs leading to discontinuation, and AESI will be provided in each period and across study periods by the upadacitinib doses as well.

For laboratory and vital signs, mean change from Baseline will be summarized in each period and percentage of subject with evaluations meeting criteria for pre-defined Potentially Clinically Significant values will be summarized in each period and across study periods by the upadacitinib doses. For selected laboratory parameters, a shift table analysis will be provided in each period and across study periods by the upadacitinib doses.

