#### 10.2.2 Adverse Event Overview

The number and percentage of subjects experiencing TEAEs will be summarized for each treatment group for the following AE categories:

- Any TEAE
- Any treatment-emergent serious adverse events (SAE)
- Any TEAE leading to discontinuation of study drug
- Any severe TEAE (Grade 3 and above according to National Cancer Institute (NCI) Common Terminology Criteria for Adverse Events (CTCAE), version 5.0)
- Any TEAE with reasonable possibility of being drug related
- Any treatment-emergent SAE with reasonable possibility of being drug related
- Any TEAE leading to death
- All Deaths
  - $\circ$  Deaths occurring  $\leq 30$  days after last dose of upadacitinib
  - Deaths occurring > 30 days after last dose of upadacitinib
  - o Related to COVID 19

In addition, a separate overview of AESIs and overview of AESIs per 100 patient-years of exposure will be provided for the categories in Section 10.2.6.

[figure not shown]

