# **Appendix B.** Definition of Adverse Events of Special Interest

Adverse Events of Special Interest (AESI) will be identified using the following search criteria (**Note:** for each database lock, the categories of AESIs will follow the latest version of Product Safety Statistical Analysis Plan for Upadacitinib, with the exceptions of Hepatitis B Reactivation which is not an AESI. AESIs with the corresponding code for the current MedDRA version in that DBL will be shown in a summary table):

[figure not shown]

AESI	Type of MedDRA Query	Broad or Narrow Search	SMQ/CMQ Search Criteria
Serious Infections	CMQ		"Infections" – Subset for SAEs
Opportunistic Infection excluding tuberculosis and herpes zoster	CMQ		"Opportunistic Infection excluding tuberculosis and herpes zoster"
Possible malignancy	SMQ	Narrow	"Malignancies"
Malignancy	SMQ	Narrow	"Malignant Tumours"
Non-Melanoma Skin Cancer (NMSC)	SMQ/CMQ	SMQ Narrow	Skin Malignant Tumours (Narrow SMQ) removing Melanoma CMQ
Malignancy excluding NMSC			Malignancy Tumours Narrow SMQ and removing NMSC output
Lymphoma	SMQ	Broad	"Malignant Lymphomas"
Hepatic Disorder	SMQ	Narrow	"Drug Related Hepatic Disorders"
Adjudicated Gastrointestinal Perforations	Medical review of events identified by the "Gastrointestinal Perforation" SMQ Narrow search		
Anemia	CMQ		"Non-Hemolytic and Non- Aplastic Anemias"
Neutropenia	CMQ		"Hematological Toxicity – Neutropenia"
Lymphopenia	CMQ		"Hematological Toxicity – Lymphopenia (Upadacitinib Product Specific)"
Herpes Zoster	CMQ		"Herpes Zoster"
Renal Dysfunction	SMQ	Narrow	"Acute Renal Failure"

AESI	Type of MedDRA Query	Broad or Narrow Search	SMQ/CMQ Search Criteria
Active Tuberculosis	CMQ		"Active Tuberculosis"
Adjudicated cardiovascular events a	Output from CAC		
MACE*			
Cardiovascular Death			
Non-fatal Myocardial Infarction			
Non-fatal Stroke			
Other Adjudicated Cardiovascular Events			
Undetermined/Unknown Cause of Deaths			
Adjudicated Thrombotic Events	Output from CAC		
VTE**			
Deep Vein Thrombosis			
Pulmonary Embolism			
Other Venous Thrombosis			
Arterial Thromboembolic Events (non-cardiac, non- neurologic)			

- CAC Cardiovascular Adjudication Committee; CMQ company MedDRA query; PT preferred term; SMQ standard MedDRA query
- \* MACE: Major Adverse Cardiovascular Events, defined as cardiovascular death, non fatal myocardial infarction and non fatal stroke.

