- \*\* VTE: Venous thromboembolic events, defined as deep vein thrombosis (DVT) and pulmonary embolism (PE) (fatal and non fatal).
- a. Reviewed and adjudicated by an independent Cardiovascular Adjudication Committee in a blinded manner.

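### SAP 10.2.6, and so the two AESI overviews in 10.2.2, carries only VTE from a thrombotic AESI that Protocol 6.1 and SAP Appendix B define more broadly

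*SAP*

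**What the plan says.** **Protocol.** The AESI list in 6.1 includes "Adjudicated embolic and thrombotic events (non-cardiac, non-CNS" (the closing bracket falls outside the quote). The entry is not limited to venous events. Sections 5.5 and 6.2 name arterial thrombosis beside the two main venous events as a reason to stop study drug. The trigger in 5.5 reads "Confirmed diagnosis of deep vein thrombosis (DVT), pulmonary embolus (PE) or non-cardiac, non-neurologic arterial thrombosis". Section 7.5 promises numbers, percentages and events per 100 patient-years, and its list of what is covered ends "deaths, AEs leading to discontinuation, and AESI will be provided in each period and across study periods by the upadacitinib doses as well".

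**SAP.** The AESI list in 10.2.6 has one thrombotic entry, "Adjudicated VTE". The footnote to Appendix B defines it: "VTE: Venous thromboembolic events, defined as deep vein thrombosis (DVT) and pulmonary embolism (PE) (fatal and non fatal". Section 10.2.2 takes its table categories from that list: a separate AESI overview and an "overview of AESIs per 100 patient-years of exposure will be provided for the categories in Section 10.2.6".

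Appendix B is broader than 10.2.6. Under a parent category of adjudicated thrombotic events it has rows for VTE, its two components, other venous thrombosis, and "Arterial Thromboembolic Events" of the non-cardiac, non-neurologic kind. Section 14.1, on changes from the protocol's analyses, is marked as not applicable.

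**The concern.** The list that drives the AESI overviews is narrower than both the protocol's AESI and the SAP's own appendix. An arterial thromboembolic event, or a venous thrombosis that is neither DVT nor PE, would be adjudicated and would be an AESI by protocol, yet would have no line in the table where a reader looks for thrombotic AESIs by dose.

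The error would run in one direction: the thrombotic AESI count and rate would be too low for the group in which the event occurred. Safety of escalation and of reduction is part of the primary objectives (Protocol 3.1). Thrombosis in general, not only venous, is among the risks named in Protocol 2.2. There is no independent data monitoring committee (Protocol 5.10), so these final summaries carry more weight.

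**Working it through.** **Text comparison**

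| Event type | Protocol 6.1 AESI | SAP 10.2.6 (drives 10.2.2) | SAP Appendix B |
|---|---|---|---|
| DVT, PE | covered | covered, as VTE | row |
| Other venous thrombosis | covered | no entry | row |
| Arterial thromboembolic, non-cardiac and non-CNS/non-neurologic | covered | no entry | row |

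The indentation of the Appendix B table cannot be seen in the text available, so other venous thrombosis could look like a sub-row of VTE. The footnote settles this, because it names only DVT and PE.

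Section 10.2.6 refers to Appendix B for search criteria, while 10.2.2 refers to 10.2.6 for table categories. A row in Appendix B does not guarantee a tabulated row: possible malignancy is in Appendix B, but 10.2.6 says it is listed only. So the SAP does not make clear which list defines the overview rows.

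**Size of one event**

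The plan gives no figure for patient-years or expected thrombotic events. Inputs from Protocol 7.6 and SAP 2.4: 454 subjects randomised 1:1, so 227 per sub-study; at most 8% dropout per 12 weeks; 54% non-responders in SS1; 65% responders in SS2. I apply these shares to subjects who reach Week 12.

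The single-blind safety populations contain everyone dosed in that period (SAP 4.0), so the base is Week 12 entrants: 227 × 0.92 = 208.84 per sub-study. With each entrant counted for 84 days:

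- patient-years = n × 84 / 365.25
- rate for one event = 100 / patient-years

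| Cohort | Entrants | Patient-years | One event per 100 PY |
|---|---|---|---|
| SC1 (15 to 30 mg) | 208.84 × 0.54 = 112.8 | 25.9 | 3.9 |
| SC2 (15 mg continued) | 208.84 × 0.46 = 96.1 | 22.1 | 4.5 |
| SC3 (30 mg continued) | 208.84 × 0.35 = 73.1 | 16.8 | 5.9 (5.95 unrounded) |
| SC4 (30 to 15 mg) | 208.84 × 0.65 = 135.7 | 31.2 | 3.2 |

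The range is about 3.2 to 6.0. Counting only Week 24 completers (a further factor of 0.92) gives SC1 23.9, SC2 20.3, SC3 15.5 and SC4 28.7 patient-years, hence 3.5 to 6.5 across cohorts and 4.2 in SC1. That base leaves out the partial exposure of dropouts, so it is the less suitable one.

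In the double-blind tables the same event weighs less: at most 227 × 84 / 365.25 = 52.2 patient-years per arm, so 100 / 52.2 = 1.9 per 100 patient-years.

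**The case against.** A reader might infer that arterial thrombosis drops out of the safety reporting, or out of all AESI rate tables. The documents do not support that, for four reasons.

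- Appendix B is the SAP's definition of AESIs, and it keeps arterial and other venous events. The SAP has not removed the AESI; a short list disagrees with its own appendix.
- Appendix B also says that the AESI categories at database lock follow the latest upadacitinib product-safety analysis plan. That plan is not in the documents, so the final rows cannot be known from here.
- Only the two overviews in 10.2.2 are expressly tied to the 10.2.6 list. The lines for TEAEs of special interest in 10.2.3 and 10.2.4 are not limited in that way.
- Protocol 6.2 states that if "non-cardiac, non-neurologic arterial thrombosis is confirmed, the subject must be discontinued from study drug". Such an event therefore also enters SAP 10.2.5: an individual listing, a summary by system organ class and preferred term, and a rate per 100 patient-years at that level by treatment group.

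All four stand, and they shrink the consequence. They do not remove the mismatch. The 10.2.5 output is not grouped as an adjudicated thrombotic category, and Protocol 7.5 promises AESI summaries as well as summaries of events leading to discontinuation. If the external plan restores the rows, 10.2.6 is wrong as written; if it does not, the protocol's AESI has been narrowed without being declared.

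A reader might also extend the point to cardiovascular events, since 10.2.6 lists only MACE. That is weaker: Protocol 6.1 gives MACE as its own example of the category.

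**Conclusion.** The point holds as a minor inconsistency in the safety tables. Read literally, the AESI overview and its version per 100 patient-years have no row for arterial thromboembolic events or other venous thrombosis, although Protocol 6.1 and SAP Appendix B include them, and SAP 14.1 declares no change. If such an event occurred, those two tables would understate the thrombotic AESI count and rate for the group concerned.

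One event would be about 3.2 to 6.0 per 100 patient-years in a single-blind cohort, and about 3.9 in SC1. This rests on the planned N, the assumed Week 12 response shares, 8% dropout, and 84 days for every entrant. It is the weight of one event if it happens; the documents give no basis for how likely that is.

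The documents do not show that the events would be missing from the final report.

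**What to change.** In SAP 10.2.6, replace the VTE entry with the protocol's full category of adjudicated embolic and thrombotic events (non-cardiac, non-CNS). Give it three sub-rows matching Appendix B: VTE, other venous thrombosis, and arterial thromboembolic events. The 10.2.2 overviews then follow without further edits. Optionally, add Appendix B's row for other adjudicated cardiovascular events beside MACE.

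If the narrowing to VTE is intended, declare it in 14.1 with the reason.

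The cost is a few rows in tables already planned. Appendix B already takes these events from adjudication committee output, so no new data or adjudication is needed.

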### 10.3 Analysis of Laboratory Data

Data collected from central and local laboratories, including additional laboratory testing due to an SAE, will be used in all analyses, except for Baseline where SAE-related laboratory assessments on or before the first dose of study drug will be excluded. The clinical laboratory tests defined in the protocol operations manual (e.g., hematology and clinical chemistry) will be summarized.

[figure not shown]
For the analysis of laboratory data, values observed up to 30 days after the last dose of upadacitinib will be included.

# Analysis of Quantitative Laboratory Parameters (Hematology, Chemistry and Urinalysis)

Raw values and change from Baseline (percent change if applicable) to each applicable post-baseline visit will be summarized for selected laboratory variables in the Safety 1 and Safety 2 Populations. At each visit, the following descriptive statistics will be presented by treatment groups: number of observations, Baseline mean (Standard deviation, SD), visit mean (SD), medium, change from Baseline mean (SD), standard error, and the 95% confidence interval of the mean change from Baseline.

#### **Shift Table Analyses**

Selected laboratory parameters will be tabulated using shift tables from Baseline to the worst value by NCI CTCAE in DB Period for the Safety 1, in SB Period for the Safety 2 Population and during the administration of upadacitinib for the All UPA Population.

Selected lipid parameters will be summarized using National Cholesterol Education Program (NCEP) Adult Treatment Panel III (ATPIII) guidelines and details can be found in Appendix E. Similar shift tables will be provided to summarize shifts from Baseline to the final post-baseline value in DB Period for the Safety 1, in SB Period for the Safety 2 Population and during the administration of upadacitinib for the All UPA Population. Here, the Upadacitinib Baseline is defined as the last observation prior to the first dose of upadacitinib. The criteria in shift table are defined using CTCAE 4.03.

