2.2 Benefits and Risks to Subjects

In the EU SmPC, upadacitinib has been approved for the treatment of moderate to severe AD in adults and adolescents 12 years and older who are candidates for systemic therapy.⁹

In adults, the recommended dose of upadacitinib is 15 mg or 30 mg QD based on individual patient presentation. A dose of 15 mg is recommended for patients at higher risk of venous thromboembolism, major adverse cardiovascular events (MACE), and malignancy. A dose of 30 mg may be appropriate for patients with high disease burden who are not at higher risk of venous thromboembolism, MACE, and malignancy or patients with an inadequate response to 15 mg. The lowest effective dose to maintain response should be used.⁹

For patients ≥ 65 years of age the recommended dose is upadacitinib 15 mg QD.⁹ The above indication and posology correspond to the European Union and may vary within different jurisdictions.

The efficacy and safety of upadacitinib 15 mg and 30 mg QD was assessed in 3 Phase 3 randomized, double-blind, multicentre studies (MEASURE UP 1, MEASURE UP 2 and AD UP)^{7,8} in a total of 2584 subjects (12 years of age and older). A significantly greater proportion of subjects treated with upadacitinib 15 mg or 30 mg QD achieved validated Investigator's Global Assessment for AD (vIGA-AD) 0 or 1, EASI 75, EASI 90, EASI 100, Dermatology Life Quality Index (DLQI) 0 or 1, or a ≥ 4-point improvement on the Worst Pruritus Numerical Rating Scale (NRS) compared to placebo at Week 16. Rapid improvements in skin clearance and itch were also achieved. Results at Week 16 were maintained through Week 52 in subjects treated with upadacitinib 15 mg or 30 mg QD.

Adverse events (AEs) such as infections including herpes zoster, major adverse cardiovascular events (MACE defined as cardiovascular death, non-fatal myocardial infarctions and non-fatal strokes), thrombosis, malignancies, hypersensitivity (serious anaphylactic reaction and angioedema), gastrointestinal perforation, bone fractures, and some laboratory abnormalities have been observed in patients receiving JAK inhibitors including upadacitinib.

An increased risk of infection including opportunistic infections (e.g., mucosal candida infections) and herpes zoster, non-melanoma skin cancer (NMSC), and abnormal laboratory changes have been observed (e.g., elevations of serum transaminases, lipids, creatine phosphokinase [CPK], and reductions in hemoglobin and neutrophils with upadacitinib therapy.

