3.5 Safety Endpoints

Safety will be assessed by AE monitoring, physical examination, vital signs, and clinical laboratory testing during the study. Laboratory assessments will include hematologic parameters, chemistry, liver function tests, and lipid parameters.

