4 INVESTIGATIONAL PLAN

4.1 Overall Study Design and Plan

This is a Phase 3b/4, randomized, blinded, treat-to-target, dose-flexibility, multi-center study that will evaluate upadacitinib, as monotherapy, in approximately 454 adult subjects (≥ 18 and < 65 years of age) with moderate to severe AD who are candidates for systemic therapy.

The study is comprised of a 35-day Screening Period, a 12-week double- blind period and a 12-week single-blind period. During the single-blind period, subjects will be blinded to the upadacitinib dose and EASI score evaluations.

The study treatment duration will be 24 weeks.

After the last study visit, a 30-day follow-up visit (or phone call if a visit is not possible) will be completed to determine the status of any new or ongoing AEs/SAEs and concomitant medications.

Subjects who meet the eligibility criteria will be randomized in a 1:1 ratio to enter SS1 to receive oral doses of upadacitinib 15 mg QD at Baseline or SS2 to receive oral doses of upadacitinib 30 mg QD at Baseline.

- SS1:
 - Subjects randomized to enter the SS1 at Baseline will receive oral doses of upadacitinib 15 mg QD during the 12-week double-blind period.

- At Week 12, subjects from SS1 receiving upadacitinib 15 mg QD will be reassigned based on their EASI response, which is calculated based on the observed EASI values regardless of the use of rescue medications:
 - Subjects achieving a < 90% reduction in EASI (< EASI 90) will be allocated to receive oral doses of upadacitinib 30 mg QD. This constitutes the Study Cohort 1 (SC1).
 - Subjects achieving a ≥ 90% reduction in EASI (≥ EASI 90) will continue to receive oral doses of upadacitinib 15 mg QD. This constitutes the Study Cohort 2 (SC2).

SS2:

- Subjects randomized to enter SS2 at Baseline will receive oral doses of upadacitinib 30 mg
 QD during the 12-week double-blind period.
- At Week 12, subjects from SS2 receiving upadacitinib 30 mg QD will be reassigned based on their EASI response, which is calculated based on the observed EASI values regardless of the use of rescue medications:
 - Subjects achieving < EASI 90 will continue to receive oral doses of upadacitinib 30 mg
 QD. This constitutes the Study Cohort 3 (SC3).
 - Subjects achieving ≥ EASI 90 will be allocated to receive oral doses of upadacitinib 15 mg
 QD. This constitutes the Study Cohort 4 (SC4).

[figure not shown]
The final and only database lock will occur at the end of the study.

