Central Laboratory Tests Clinical Chemistry, Hematology	✓	✓	✓	✓	✓	✓	✓	√	✓
TB Test (QuantiFERON-TB Gold Plus test [or interferon gamma release assay (IGRA) equivalent such as T-SPOT test] and/or local PPD skin test, if required)	1								

Activity	Screening	Baseline	Week 4	Week 12	Week 16	Week 24	Unscheduled Visit	Premature Discontinuation Visit	30-day Follow Up Visit
	D-35 to D -1	D1	D 29	D 85	D 113	D 169			
Visit Window (days)			+3 +3	+3	+3	+3			8 +I
Central Lab- HIV Screening, Hepatitis B and C Screening	✓								
Randomization/Drug assignment		✓		✓					
Dispense Study Drug		✓	✓	✓	✓				
Review and copy investigational product administration information from subject paper diary cards for China sites only			*	✓	V	*	1	*	
Optional biomarker samples: Whole blood DNA		✓							
Optional biomarker samples: Plasma/serum proteomic		✓	✓	✓	✓	✓	✓	*	
Optional biomarker samples: PBMC		✓	✓	✓					
Dispense wearable tool (Substudy Only)	✓								
Subject uses wearable tool for 7 nights prior to Baseline and following Visit (Substudy Only)		✓	✓	V	V				
Collect wearable tool (Substudy Only)						✓		✓	

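### The lipid shift tables take the final value from a window that runs 30 days past the last dose, so follow-up visit timing can decide whether Week 24 or an off-drug sample is used

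*SAP*

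**What the plan says.** SAP 10.3 has two kinds of laboratory shift table. For the general parameters: "Selected laboratory parameters will be tabulated using shift tables from Baseline to the worst value by NCI CTCAE". For the lipid parameters, grouped by the ATP III categories in SAP Appendix E: "Similar shift tables will be provided to summarize shifts from Baseline to the final post-baseline value". The lipid tables are planned for the double-blind period (Safety 1), the single-blind period (Safety 2) and ALL UPA.

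The opening of SAP 10.3 sets one inclusion rule for all of these: "For the analysis of laboratory data, values observed up to 30 days after the last dose of upadacitinib will be included".

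In Protocol Appendix D, the row "Central Laboratory Tests Clinical Chemistry, Hematology" is ticked in all nine columns, the last being the 30-day Follow Up Visit. Protocol 3.5 makes lipids part of the laboratory data: "Laboratory assessments will include hematologic parameters, chemistry, liver function tests, and lipid parameters". The schedule has no separate lipid row. On follow-up, Protocol 4.1 says: "After the last study visit, a 30-day follow-up visit (or phone call if a visit is not possible) will be completed".

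Nothing in SAP 10.3 restricts the final value to samples taken on treatment or to a named visit.

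**The concern.** A 30-day tail suits a worst-value table, where an extra sample can only leave the result unchanged or make it worse. In a last-value table the extra sample displaces the one before it. For a completer, the last sample on or close to treatment is Week 24, and the follow-up sample comes about a month later.

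The day-30 limit also falls inside the follow-up visit window. A sample on day 30 counts and becomes the final value; a sample on day 31 is dropped and Week 24 stands. A phone follow-up yields no sample, and Week 24 stands again. The table would then mix on-drug and off-drug values according to scheduling.

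This matters because Protocol 2.2 names lipids among the laboratory effects of the drug: "abnormal laboratory changes have been observed (e.g., elevations of serum transaminases, lipids". The study is meant to inform the use of 15 mg and 30 mg, and the single-blind and ALL UPA tables are where lipid shifts are set out by dose after Week 12. If lipids fall after stopping, those tables lean towards showing no shift.

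**Working it through.** The documents give no figure for this point, so there is none to reproduce. The check follows the selection rule through the visit schedule and then sizes it under stated assumptions.

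**Which value is selected**

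1. Rule: the latest post-baseline value (SAP 10.3, lipid shift tables).
2. Eligible values: up to day 30 after the last dose (SAP 10.3, opening).
3. Latest scheduled chemistry sample: the 30-day Follow Up Visit (Protocol Appendix D).
4. Taken literally, a follow-up sample on or before day 30 is the final value. Otherwise Week 24 is.

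**Share of follow-up samples inside the window**

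Inputs: a follow-up window read as ±3 days (Appendix D; the row is partly garbled in the text available). Assumption: visit days are spread evenly.

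- Last dose on the Week 24 visit day: follow-up falls on days 27 to 33. Days 27, 28, 29 and 30 count, so 4/7 = 57%.
- Last dose the day before: follow-up falls on days 28 to 34. Days 28, 29 and 30 count, so 3/7 = 43%.

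**Number of completers affected**

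Inputs: N = 454 and 8% dropout per 12 weeks, taken at its stated maximum (Protocol 7.6, SAP 2.4).

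- Expected completers = 454 × 0.92² = 384.
- All attend on site: 384 × 3/7 = 165 to 384 × 4/7 = 220.
- Half attend on site (assumed): 82 to 110, that is 3/14 = 21% to 4/14 = 29% of all completers.

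**Effect on the table**

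Reported shift = true Week 24 shift × (1 − share displaced × share reverted). The true shift of 20% and the reversion shares are assumptions, because the documents give neither.

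| Share displaced | No reversion | 25% revert | 75% revert |
|---|---|---|---|
| 3/7 (43%) | 20% | 0.20 × (1 − 0.429 × 0.25) = 17.9% | 0.20 × (1 − 0.429 × 0.75) = 13.6% |
| 4/7 (57%) | 20% | 0.20 × (1 − 0.571 × 0.25) = 17.1% | 0.20 × (1 − 0.571 × 0.75) = 11.4% |

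These rows assume full on-site attendance. With half attending, the extremes are 0.20 × (1 − 0.214 × 0.25) = 18.9% and 0.20 × (1 − 0.286 × 0.75) = 15.7%.

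**Which tables are touched**

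The single-blind and ALL UPA tables are. The double-blind table is not affected for subjects who enter the single-blind period, whose final value there is about Week 12. Subjects who stop during the double-blind period could be affected.

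**The case against.** **Lipids at follow-up are inferred.** Protocol 3.5 lists lipids as an item beside chemistry, and SAP 10.3 refers to the Operations Manual for the test list. The lack of a lipid row proves little: SAP 10.3 also mentions urinalysis, which has no row either. This stands. If lipids are not drawn at follow-up, the issue disappears for completers.

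**The period labels might exclude follow-up.** The lipid sentence ties its tables to the single-blind period and to the administration of upadacitinib. Protocol 7.5 treats the end of a period as distinct from 30 days after the last dose. So Week 24 could be the intended final value. This shows that the text can be read two ways, but it does not settle the matter. SAP 10.2.1 runs both labels to 30 days after the last dose for treatment-emergent events, and SAP 10.3 applies the same 30 days to laboratory data without exception. A programmer following the SAP could well include the follow-up sample.

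**Reversal is assumed.** A reader might infer that the tables will understate lipid increases. The documents do not support that: Protocol 2.2 reports elevations and says nothing about what happens after stopping. Nor do they support saying that most completers are displaced. The share depends on the last-dose day, the spread of visit days and the number of phone follow-ups.

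**Other outputs limit the harm.** By-visit summaries are planned for selected laboratory variables, and SAP Appendix D counts extreme lipid values. This stands in part. The by-visit summaries cover Safety 1 and Safety 2 only and show no category shifts. The Appendix D limits are 10.34 mmol/L for total cholesterol and 5.7 mmol/L for triglycerides, against top ATP III cuts of 6.21 and 2.26. LDL and HDL have no such limit. The study is also descriptive, so no test is at risk.

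**Conclusion.** The point holds as a flaw in the selection rule. Read together, SAP 10.3 and the Activity Schedule let visit timing decide whether a completer contributes an on-drug or an off-drug lipid value, provided that lipids are in the follow-up panel. Mixing the two makes the table hard to interpret whatever lipids do after stopping.

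The size is conditional. About 43% to 57% of completers with a follow-up sample would be displaced, or 21% to 29% of all completers if half attend on site, given evenly spread days in a ±3-day window. The fall from an assumed 20% to about 18% to 11% illustrates 25% to 75% reversion with full attendance; it is not a forecast. With no reversion the table shows the true figure. The correction is cheap and worth making, but the documents do not show that lipid increases will be understated.

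**What to change.** In SAP 10.3, define the final value for the lipid shift tables as the last post-baseline value up to and including the end-of-treatment visit of the period. That is Week 12 or Week 24 for completers, and the Premature Discontinuation visit for subjects who stop early. Exclude the 30-day follow-up sample from these tables and show it separately as off-drug. Keep the 30-day window for the worst-value CTCAE shift tables and the potentially clinically important tables. Confirm against the Operations Manual whether lipids are drawn at follow-up.

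The cost is a sentence in the SAP, one changed derivation and a small added display. No new data are needed, and the only database lock is at the end of the study.

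The downside is a small remaining off-drug component. Protocol 5.6 asks for the Premature Discontinuation visit preferably within 2 weeks, so some of those samples will be drawn up to about 2 weeks after the last dose. A strict cut at 1 day after the last dose, such as SAP 7.2 uses for concomitant medication, is not advised. It would drop those samples, and it could remove subjects who stop before Week 4 altogether, because they have no earlier scheduled post-baseline sample.
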